Fig. 4 Hepatic triglyceride content during the cholic acid study. Connected open circles represent the 12 subjects who completed both the six month study periods. For three subjects with incomplete data, filled symbols represent subjects with placebo data only; inverted triangles represent 3 month data. Median values for each phase are shown as horizontal bars.

3. Concise Summary of Project:

This study will be a randomized, double-blind, placebo-controlled, cross-over trial (Fig. 5). Patients who are considered eligible for the study will undergo screening evaluation to determine their eligibility for the trial. For those who are found to be eligible, during the baseline period, they will continue their usual diet and other lifestyle measures without changing any medications for 1 month in order to establish a baseline state. Three blood samples will be obtained during this period at the Clinical and Translational Research Center. Following the baseline period, the patients will receive obeticholic acid (OCA) or an identical placebo in the dose of 25 mg/day for a period of 4 months and then will receive the other treatment (OCA or placebo) for 4 months. There will be a wash-out period of 4 months in-between the two study periods. The dose of OCA is chosen based upon several considerations: a. In a previous study of patients with type 2 diabetes mellitus and hepatic steatosis, this dose resulted in significant improvement in insulin-mediated glucose disposal and reduction in ALT and GGT (49). b. This dose is generally well-tolerated with negligible side effects. If there are intolerable side effects which are considered probably or possibly related to OCA/placebo, the dose of OCA/placebo will be reduced to 25 mg every other day. If the side effects persist despite reduction of the dose, the medication will be stopped but the subject will continue to participate and complete the trial (as per intent to treat protocol).

[figure not shown]

Fig. 5 : Study design and time points for determination of variables. Wash out period will be for 4 months.

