Patients will be educated to maintain their usual physical activities and diet during the study. The subjects will be admitted to the Clinical and Translational Research Center for the baseline evaluations (at the beginning of the two study periods), and at the end of four months during each study period. In some subjects, unable to visit CTRC at the end of 2 months, we will provide kits to them for mailing the blood and urine samples using courier service. We have done such collections successfully in our previous trials of leptin therapy in patients with lipodystrophies.

Justification for the choice of design: We considered both the randomized, parallel design and the cross-over design. In view of the rare prevalence of FPLD, we decided to use the cross-over design. This allows us to achieve more power with fewer patients compared to the parallel design. We do not expect carry over effects of OCA on hepatic triglyceride levels given that there will be a four month wash-out period between the two study periods and an additional 4 month time before determining the end point variable during the second study period. We will attempt to keep the drop-outs to as minimum as possible to achieve maximum out of this design. Our choice of study design was guided by Lagakos's editorial entitled, "Clinical Trials and Rare Diseases" (58).

Primary and Secondary Endpoint Variables: The primary end-point variable will be the reduction in the liver TG content on ¹H MRS. Reductions in the levels of serum alanine and aspartate aminotransferases, gammaglutamyl transpeptidase, triglycerides, insulin and suppression of hepatic glucose output during the low-dose and high-dose insulin infusions during the euglycemic clamp study (measure of hepatic insulin sensitivity) will STU062014-033, [name], Form A, Mod_8, 08-02-19 Protocol version number 1, 08042014

Page 6 of 24

be the secondary end-points of the study. Complete blood counts and serum chemistries will be performed for safety considerations. As an evidence of FXR activation, fasting serum FGF19 levels will be measured. We will also measure liver size using magnetic resonance imaging. These additional tests will be performed at baseline and after 2 and 4 months of therapy.

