The potential benefit of obeticholic acid therapy is an improvement in hepatic steatosis as demonstrated by ¹H MRS of the liver, as well as possible improvement in raised levels of hepatic enzymes such as transaminases and improved insulin sensitivity. Reduction in hypertriglyceridemia will be shown through improved fasting serum triglyceride levels. The results of this study may help define a safe and effective treatment for non-alcoholic hepatic steatosis in people with lipodystrophy.

13. Biostatistics:

Power and sample size: The primary endpoint variable is the difference in hepatic triglyceride concentration between OCA and Placebo after four months of each treatment. Sample size estimates are based on our preliminary data with a geometric mean hepatic triglyceride concentration of 16% in 29 patients with FPLD who have hepatic triglyceride concentration >5.6% and a corresponding coefficient of variation of 25% based on log transformed data. We expect a reduction in hepatic fat of at least 25% (i.e., reduction from 16% to 12% liver fat with OCA) and calculate, for an alpha of 0.05 and power of >0.90, we will need 16 patients for the study. Allowing for a 20% drop-out rate, a total of 20 patients will be required. The drop-out rate is estimated from our recent studies in patients with FPL (18, 71).

Randomization: The sequence of OCA and placebo treatment will be determined by blocked randomization.

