Statistical analysis: Descriptive statistics and 95% confidence intervals will be used to summarize responses to OCA and Placebo treatment and treatment differences of this crossover study. For hepatic triglyceride concentration, mixed linear repeated measures models will be constructed to compare OCA versus Placebo after four treatment months and to evaluate treatment sequence effects. Secondary endpoint variables will be FGF19 levels, hepatic insulin sensitivity measurements from the euglycemic, hyperinsulinemic glucose clamp, serum triglycerides, insulin, and aminotransferase levels and will be analyzed with similar mixed linear repeated measures models. Two month treatment response comparisons, gender subgroup interactions, per-protocol hepatic triglyceride concentration responses will be assessed as secondary analyses. The primary and secondary endpoints, which are likely to be skewed, will be log transformed prior to analysis, as appropriate. Nonparametric tests will be implemented, if necessary, to satisfy analysis assumptions. Exploratory analyses: Delta responses (OCA-Placebo) will be computed for primary and secondary variables and the association among the delta variables will be evaluated with Spearman correlation coefficients. A two-sided p value of <0.05 will be considered statistically significant. No interim analysis is planned because of the relatively short study duration and limited sample size. SAS (SAS Institute,

Page 17 of 24

Cary, NC) statistical software will be used; particularly SAS PROC MIXED will be used for repeated measures models. The data will be analyzed according to intention-to-treat principles; our mixed model analysis approach can accommodate certain types of missing data. If a subject is unable to complete or tolerate the intervention in either blinded treatment period, we will continue follow-up if possible or the post-treatment and other final measurements may be made prior to 4 months to minimize missing outcome data.

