Criteria for Discontinuing Drug/Placebo: Patients will be carefully recruited and screened to maximize retention. A proactive retention plan will be in place for study personnel to stay in close contact with study subjects. We will continue to follow patients and encourage patients to return for follow up evaluation regardless of adherence to protocol. The study drug/placebo will be discontinued as necessary, for safety reasons particularly if the patients report serious adverse reactions. Patients developing serious acute medical conditions, which in the opinion of the investigators will interfere with subjects continued participation, will be withdrawn from the drug/placebo as well as women who become pregnant.

Study Stopping Criteria:

• For individual subject: In the event of a single subject CTCAE Grade 3 (severe AE) or higher adverse event, regardless of whether it is attributed to OCA unless it is caused by an accident that could not reasonably be attributable to the drug.

• For all subjects: In the event of two or more subjects experiencing a CTCAE Grade 3 or higher adverse event, regardless of whether it is attributed to OCA unless it is caused by an accident that could not reasonably be attributable to the drug.

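### Could an early final scan displace the month-4 primary outcome in a patient who has stopped study drug?

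*Combined protocol and SAP*

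**What the plan says.** The trigger sentence is in section 13 (Biostatistics), at the end of the Statistical analysis text. It opens "If a subject is unable to complete or tolerate the intervention in either blinded treatment period" and continues "we will continue follow-up if possible or the post-treatment and other final measurements may be made prior to 4 months". Its closing words give the aim: to keep missing outcomes to a minimum. Just before it, the plan commits to intention-to-treat analysis and notes that the mixed model tolerates some missing data.

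The primary endpoint, under Power and sample size, is the "difference in hepatic triglyceride concentration between OCA and Placebo after four months of each treatment". The primary model is to "compare OCA versus Placebo after four treatment months".

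Three other places deal with patients who stop drug or with the visit schedule:

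- Section 3 (Concise Summary of Project), on side effects that persist after dose reduction: "the medication will be stopped but the subject will continue to participate and complete the trial (as per intent to treat protocol").
- Section 3, on admissions: at the start of each study period "and at the end of four months during each study period".
- Section 13, Criteria for Discontinuing Drug/Placebo: "We will continue to follow patients and encourage patients to return for follow up evaluation regardless of adherence to protocol".

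**The concern.** The condition for an early final scan is drug status. A patient can be off drug and still able to travel to the month-4 admission, and the plan expects such patients because it provides for stopping drug on safety grounds while follow-up continues. The two responses are joined by a bare *or*, and nothing limits the early scan to patients who will not come back. Nor does the plan say which scan is analysed if both exist, or how an early-only scan enters a comparison defined at four months.

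If an early scan replaced month 4 in a patient who had stopped OCA, and liver fat rose again off drug, the estimate would move from the month-4 intention-to-treat quantity toward an on-drug effect. Measured against the full four-month on-treatment effect, the same scan would understate, because treatment was cut short. With about 16 to 20 patients, each outcome carries visible weight.

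**Working it through.** **Step 1: the plan's own figure.** Inputs from Power and sample size: a reduction from 16% to 12% (ratio 0.75), CV 25%, alpha 0.05 (two-sided, from Statistical analysis), power above 0.90. I read the CV as within-patient. That is an assumption, since the text ties it to concentrations in 29 patients.

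- Log effect: d = −ln(0.75) = 0.2877.
- Within-patient log SD: √ln(1 + 0.25²) = 0.2462. SD of a paired difference: √2 × 0.2462 = 0.3482.
- n = [(1.960 + 1.282) × 0.3482 / 0.2877]² = 15.4, so 16. Then 16 / 0.8 = 20, matching "Allowing for a 20% drop-out rate, a total of 20 patients will be required".

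The figure reproduces under the normal approximation and does not depend on the early-scan sentence.

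**Step 2: the texts side by side.**

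| Question | What the plan gives |
|---|---|
| Is a patient who stops drug followed? | Yes: section 3 (persistent side effects) and Criteria for Discontinuing (whatever the adherence) |
| Is a month-4 visit scheduled? | Yes, an admission in each period (section 3) |
| Which comes first in the trigger sentence? | Continued follow-up, where possible |
| Why allow an early scan? | To avoid a missing outcome |
| Is an early scan said to count as month 4? | No |

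An early scan that displaced an obtainable month-4 scan would create a missing month-4 value, which is contrary to the sentence's stated aim. The fallback reading is the one that fits every row.

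**Step 3: size if the less plausible reading were followed.** The documents give no rate of stopping drug and no time course, so everything here is assumed: 20 patients, stable placebo, a share p stopping in the OCA period at month s, all of them scanned early and none at month 4. The estimated reduction is 1 − exp(−d[(1 − p) + p·e]), where e is the fraction of the full effect present at the scan. With linear onset and waning over four months each, the early scan has e = s/4 and the month-4 scan has e = max(0, s/4 − (4 − s)/4).

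| Case, p = 4/20 | Month-4 scan | Early scan | Shift (points) | Log shift |
|---|---|---|---|---|
| s = 1 | 20.56% | 21.69% | 1.13 | 0.0144 |
| s = 2 | 20.56% | 22.81% | 2.25 | 0.0288 |
| s = 3 | 22.81% | 23.91% | 1.10 | 0.0144 |
| Extreme (early e = 1, month-4 e = 0) | 20.56% | 25.00% | 4.44 | 0.0575 |
| No waning after stopping | – | – | 0 | 0 |

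One such patient (p = 1/20) gives 0.27 to 0.55 points in the linear cases and 1.09 at the extreme.

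Standard error of the log effect: 0.3482/√16 = 0.0871, or 0.3482/√20 = 0.0779. The linear shifts are 0.0144/0.0871 = 0.17 to 0.0288/0.0779 = 0.37 standard errors; the extreme is 0.66 to 0.74. A true 25% reduction would carry a 95% interval of about 9.7% to 37.7% (n = 16) or 11.7% to 36.3% (n = 20). If the 25% instead describes paired differences, the standard errors are 0.0616 and 0.0551, the linear shifts 0.23 to 0.52, and the extreme 0.93 to 1.05.

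**Step 4: size of the gap that does remain.** Some patients will have only an early scan because they do not return. The analyst either uses that scan or leaves the value missing. In the simple case of leaving these patients out, the estimate is 25.00%, against 21.69%, 22.81% or 23.91% with the early scan: a spread of 1.1 to 3.3 points at p = 4/20. The largest log difference is 0.20 × 0.75 × 0.2877 = 0.0432, which is 0.0432/0.0779 = 0.55 standard errors (within-patient CV, n = 20). Leaving them out lies 2.2 to 4.4 points from the month-4 value; using the early scan lies 1.1 to 2.3 points from it.

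**The case for a change.** The best case for a change is that the sentence does not state the fallback reading outright. Its trigger is intolerance or non-completion, its *or* is unconditional, and no sentence ranks two scans or says how an early-only scan is modelled. All of that is true. Settling the rule before unblinding would be cheap, and the plan's expectation that side effects will cause no drop-outs does not help, because stopping drug is not the same as dropping out.

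What stands is a missing line of analysis detail. What does not stand is the suggestion that the plan invites staff to give up month-4 scans they could obtain. The feared case also needs several things at once: patients off drug and able to attend, an early scan in each, no month-4 scan, and an effect that wanes. Section 3 puts a dose reduction before stopping for side effects, and the study stopping criteria apply to all subjects once two have Grade 3 or higher events. These features narrow the scenario without excluding it, since stops for milder events remain possible. The clause covers both blinded periods, so staff cannot choose early scans by known arm. The 4-of-20 case borrows the drop-out allowance, which is not a rate of stopping drug while remaining available.

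**Conclusion.** No change is called for. Followed as written, the plan yields the month-4 value in every patient who attends, on or off drug, and treats an early scan as a substitute for an outcome that would otherwise be lost. The natural way to fill the unwritten part is to analyse the month-4 scan whenever it exists and, under the stated intention-to-treat principle, to use an early-only scan as that period's final value. Rewording would mostly repeat what section 3 and Criteria for Discontinuing already say.

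Even if the sentence were misapplied to one patient in five on OCA, the linear scenario moves the estimate by about half a standard error at most under either reading of the CV. Only the extreme assumption (full effect at the early scan, none at month 4) combined with the paired-difference reading reaches about one standard error. These sizes rest on assumed stopping rates and time courses that the documents do not supply; without waning, the shift from scan choice is zero.

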Mutational Analysis of LMNA gene: To confirm the diagnosis of FPLD, direct sequencing of the entire coding region and the surrounding intron-exon boundaries of the *LMNA* gene will be conducted in the probands from each pedigree followed by sequencing of the disease-causing variant in the rest of the family members. Primers that amplify each exon of *LMNA* from genomic DNA templates have been designed from published sequence information (69).

Monitoring of potential side effects: Biochemical testing and routine urinalysis will be done every 6 weeks, during the periods when patients are on study drug or placebo. Telephone contact will be initiated with subjects every 2 weeks to assess for symptoms such as new or worsening pruritus, abdominal pain, new or worsening fatigue, anorexia, nausea, rash, vomiting, diarrhea, jaundice (yellow skin or sclera, high amber colored urine and pale stools) and vague neuropsychiatric symptoms. For patients outside of Dallas, blood tests will be arranged every 6 weeks and if there are any abnormalities, they will be asked to either visit us in person (for those living in the Dallas area) or see their primary care physician for physical examination (for those from outside Dallas). We will communicate with their physicians about the lab data and physical examination findings.

Drug will be discontinued in subjects immediately who develop liver decompensation events (e.g., variceal bleed, hepatic encephalopathy, ascites, etc.) and will not restart the drug even if the events are resolved.

Patients will be asked to report following symptoms as it will trigger immediate evaluation of the patient for hepatic toxicity: new or worsening pruritus, abdominal pain, new or worsening fatigue, anorexia, nausea, rash, vomiting or diarrhea. Even vague neuropsychiatric symptoms have been associated with acute liver failure. If prompt evaluation is not possible, the investigational drug will be immediately discontinued.

Patients will be asked to withhold drug during intercurrent illness, such as gastroenteritis resulting in dehydration, or other reasons for dehydration, and that patients should be reevaluated with both biochemical testing and physical exam prior to restarting the drug.

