Physical exam and liver biochemistries including ALT, AST, total bilirubin, and ALP will be performed at each clinic visit and at any unscheduled visit triggered by patients reporting symptoms. If elevations in ALT, AST, total bilirubin (TB), and ALP levels trigger reevaluation, then platelet count, INR, albumin, direct bilirubin, electrolytes and creatinine will be included in repeat testing.

We will use the same Liver Laboratory Criteria for Monitoring of Suspected Hepatic Injury or Decompensation as submitted recently by Intercept Pharmaceuticals (Table 1) (Protocol 747-303 Safety Amendment).

Table 1: Liver Laboratory Criteria for Monitoring for Suspected Hepatic Injury or Decompensation

Criteria Resulting in Immediate Interruption of Investigational Product Upon First Observation		
Baseline	Upper Laboratory Threshold	Frequency of Monitoring (Repeat Testing)
Conj. bilirubin ≤ULN	≥1.5x ULN	Not applicable
	If Total Bili rise >=0.5 mg/dL,	
	reassess conjugated if >ULN	
Creatinine	>ULN AND increase by 20%	
Criteria Resulting in	Repeat Testing	
Baseline	Upper Laboratory Threshold	Frequency of Monitoring (Repeat Testing)
Key Liver Parameter	s for Hepatic Injury	
ALT ≤ULN	≥3x ULN	2-3 days
ALT >ULN and	≥3x baseline or incremental	
<2x ULN	increase from baseline >250	2-3 days
	U/L	
ALT ≥ 2x ULN	≥2x baseline or incremental	
	increase from baseline >250	
	U/L	
AST ≤ULN	≥3x ULN	2-3 days
AST >ULN and	≥3x baseline or incremental	2-3 days
<2x ULN	increase from baseline >250	
	U/L	
AST ≥ 2x ULN	≥2x baseline or incremental	
	increase from baseline >250	
	U/L	
ALP ≤ULN	≥1.5x ULN	7 days
ALP >ULN	≥1.5x baseline	7 days
Total bilirubin	≥1.5x baseline AND >ULN	2-3 days
≤ULNª		
Total bilirubin	≥1.5x baseline	2-3 days
>ULN ^a	> 000/ in an and from the action	
	≥30% increase from baseline	2-3 days
INR>ULN [♭]	>1.5 AND ≥10% increase from	2-3 days
	baseline	
GGT ≤ULN	≥3x ULN	2-3 days
GGT >ULN Other Parameters Re	≥3x baseline eflective of Overall Hepatic HealtI	2-3 days h
		···
Albumin	<3.2 g/dL	2-3 days
Platelets	<100x10 ³ /mm ³ AND ≥10%	2-3 days
	decrease from baseline	
Electrolytes ^c	Sodium <130	2-3 days

- ^a Diagnosis of Gilbert's Syndrome should be established during baseline. Conjugated bilirubin to be sole determinant in such subjects.
- ^b Does not apply in subjects on anti-coagulants
- ^c Sodium will be measured as an assessment of liver failure (hyponatremia).

Study Medication – Obeticholic Acid

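### An intolerable, drug-related Grade 3 or higher side effect falls under both the reduce-first dosing rule and the individual stopping criterion, and the protocol does not say which governs

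*Combined protocol and SAP*

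**What the plan says.** Section 3 (Concise Summary of Project) contains the dosing instructions. The first step is this: "If there are intolerable side effects which are considered probably or possibly related to OCA/placebo, the dose of OCA/placebo will be reduced". The reduced schedule is 25 mg on alternate days. The second step is this: "If the side effects persist despite reduction of the dose, the medication will be stopped but the subject will continue to participate". The trigger is tolerability plus a judgement of relatedness. No CTCAE grade is named, either as a floor or as a ceiling.

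Section 13 (Biostatistics), under Study Stopping Criteria, has one bullet that applies to a single patient. It reads: "In the event of a single subject CTCAE Grade 3 (severe AE) or higher adverse event, regardless of whether it is attributed to OCA". The bullet that applies to everyone reads: "In the event of two or more subjects experiencing a CTCAE Grade 3 or higher adverse event, regardless of whether it is attributed". Both carry the same single exception: "unless it is caused by an accident that could not reasonably be attributable to the drug". Neither bullet has a verb stating the action.

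The paragraph just before those bullets gives a third, discretionary standard. Study drug is withdrawn as needed on safety grounds, especially for serious reactions. That standard turns on seriousness rather than grade.

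Section 10 asks the monitoring committee to recommend continuing, ending or modifying the trial (item d) and to review safety against stopping rules set in advance (item e). It does not mention the two-subject criterion.

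**The concern.** An investigator faced with a severe side effect thought possibly due to the drug will find two answers. The dosing text says to halve the exposure and watch. The stopping text says this is a stopping event. The first keeps a blinded patient on study drug after a severe event; the second does not. Someone working from section 3, where the dosing rules are written, could in good faith continue drug where section 13 calls for a stop. What is at stake is patient safety and consistent handling of the same event across patients.

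The second question is smaller. When a second subject has a Grade 3 or higher event, the criterion applies to everyone, but the text does not say whether dosing is suspended or the trial ends.

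**Working it through.** The plan gives no figure on this point, so the check is a comparison of the texts.

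**Step 1. Which events meet which rule.** Section 3 needs the event to be intolerable and possibly or probably related. Section 13 needs Grade 3 or higher and not an accident unconnected with the drug.

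| Event | Section 3: reduce first | Section 13: individual criterion |
|---|---|---|
| Intolerable, related, below Grade 3 | applies | does not apply |
| Grade 3+, not intolerable (for example a laboratory change without symptoms) | does not apply | applies |
| Grade 3+, intolerable, judged unrelated, not an accident | does not apply | applies |
| Grade 3+ from an accident not attributable to the drug | does not apply | excepted |
| Grade 3+, intolerable, possibly or probably related | applies | applies |

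Only the last row is in conflict.

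**Step 2. Whether the two actions are compatible in that row.** Reduction leaves the patient on 25 mg every other day, which is 25 / 2 = 12.5 mg/day on average in the OCA period. The stopping criterion takes the patient off drug at the event. Section 13 does not say whether that is a pause or permanent, but on either reading the patient is not continued at a reduced dose at that moment. In the placebo period no active drug is involved, but the blinded investigator faces the same choice.

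**Step 3. Whether other text settles it.** Section 4 requires a permanent stop for liver decompensation ("will not restart the drug even if the events are resolved"), and Table 1 has a block headed "Criteria Resulting in Immediate Interruption of Investigational Product Upon First Observation". These decide the matter for decompensation and for the listed laboratory findings. Section 4 also requires immediate evaluation for hepatic toxicity when listed symptoms appear, and immediate discontinuation if that evaluation cannot be done promptly. They do not cover, for example, pruritus graded 3, judged possibly related and promptly evaluated with no laboratory trigger. Section 9 names pruritus as the most common non-serious adverse event with OCA. That patient is left with sections 3 and 13, and no sentence ranks them.

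**Step 4. How many patients.** The all-subjects criterion is met at the second affected subject. Before it applies, therefore, at most one subject can have had a qualifying Grade 3 or higher event: 1 of 20, or 5% of those enrolled. This bounds the conflict only up to that point.

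**Step 5. The two-subject criterion.** The documents give no Grade 3 or higher rate at 25 mg. Assume a per-subject probability p over the study and independent subjects. The chance that at least 2 of 20 have an event is 1 − (1 − p)^20 − 20p(1 − p)^19. At p = 5% this is 1 − 0.358 − 0.377 = 0.26. At 2%, 10% and 20% it is 0.06, 0.61 and 0.93. These figures count every Grade 3 or higher event. They show only that the consequence of this criterion may be needed, not how often the conflict in Step 1 arises.

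**The case against.** The strongest reply is that ordinary reading reconciles the rules. Section 3 is a summary with a general tolerability step-down. Section 13 has a dedicated, graded safety limit, and a specific limit caps a general rule. The discretionary sentence in section 13 and the safeguards in section 4 point the same way. This is probably what was intended, and the two rules do fit together if the stricter one wins. But nothing says so, and a safety rule should not have to be inferred from where it stands in the document. That part of the concern survives.

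Other parts of the reply stand and limit the point. A reader might infer that every drug-related Grade 3 event is caught in the conflict. It is not, because section 3 applies only to intolerable effects. A reader might also infer that section 13 means no drug for the rest of the period. The text does not say that the stop is permanent. Nor is the instruction on intercurrent illness ("Patients will be asked to withhold drug during intercurrent illness, such as gastroenteritis resulting in dehydration") in contradiction with section 13, since a patient can be off drug under both. Finally, the committee remit in section 10, items (d) and (e), partly covers the two-subject question. What is left there is a clarification.

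**Conclusion.** The concern holds in a narrow form. For an event that is intolerable, judged possibly or probably related, and Grade 3 or higher, sections 3 and 13 give incompatible dosing instructions with no stated precedence. The difference at the event is continued dosing at half the planned average against none, for at most one patient before the all-subjects criterion applies. This rests on reading the individual criterion as stopping study drug, which its heading and the preceding text on discontinuation support although the bullet has no verb.

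It would be tempting to read this as a threat to the trial's power. The documents do not support that: they give no Grade 3 rate, and any power figure would depend on assumptions about accrual, drop-out and the nature of the coefficient of variation that do not measure this defect. The ambiguity over suspension or termination is secondary. The wording should be corrected because it concerns safety and costs almost nothing.

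**What to change.** In section 3, state that dose reduction applies only to side effects below CTCAE Grade 3, and that at Grade 3 or higher study drug or placebo is stopped under the Study Stopping Criteria in section 13. Follow-up and outcome measurement then continue as sections 3 and 13 already provide, including the section 13 option of taking final measurements before month 4. Leave both triggers and the accident exception as they are.

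As a secondary clarification, state in section 13 whether the two-subject criterion suspends dosing pending the committee's recommendation under section 10, items (d) and (e), or ends the trial.

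The cost is a wording amendment with the usual approvals and no added visits, patients or tests. The downside is a small possible loss of on-drug data from the one patient who might otherwise have continued at the reduced dose.
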